12.1.2. Protocol Deviations

A protocol deviation is any noncompliance with the clinical trial protocol, GCP, or other study requirements (e.g., SOPs, Laboratory Manuals, etc). The noncompliance may be either on the part of the subject, the investigator, or the study site staff. As a result of deviations, corrective actions are to be developed by the site and implemented promptly.

These practices are consistent with ICH E6:

- 4.5 Compliance with Protocol, sections 4.5.1, 4.5.2, and 4.5.3
- 5.1 Quality Assurance and Quality Control, section 5.1.1

- 5.20 Noncompliance, sections 5.20.1, and 5.20.2.

It is the responsibility of the site to use continuous vigilance to identify and report deviations within 5 working days of identification of the protocol deviation, or within 5 working days of the scheduled protocol-required activity. All deviations must be addressed in study source documents and reported to the clinical study monitor or to the CRO. Protocol deviations must be sent to the IRB/EC per their guidelines. The site investigator/study staff is responsible for knowing and adhering to their IRB/EC requirements.

It is not anticipated that waivers of eligibility requirements will be granted for any subjects. However, if eligibility requirements are waived in special circumstances, waivers must be approved by the medical monitor and the sponsor before a subject may be enrolled. Documentation of granted waivers will be maintained in the investigator's and sponsor's files.

12.1.3. Publication and Data Sharing Policy

The results of this study may be published or presented at scientific meetings. The investigator agrees to submit all manuscripts or abstracts to Botanix Pharmaceuticals at least 30 days prior to submission. This allows Botanix Pharmaceuticals to protect proprietary information and to provide comments based on information from other studies that may not yet be available to the investigator.

In accordance with standard editorial and ethical practice, Botanix Pharmaceuticals will generally support publication of multicenter trials in their entirety. In this case, a coordinating investigator will be designated by mutual agreement. Authorship will be determined by mutual agreement.

12.2. Conflict of Interest Policy

The independence of this study from any actual or perceived influence is critical. Therefore, any actual conflict of interest of persons who have a role in the design, conduct, analysis, publication, or any aspect of this trial will be disclosed and managed. Furthermore, persons who have a perceived conflict of interest will be required to have such conflicts managed in a way that is appropriate to their participation in the study. The study leadership has established policies and procedures for all study group members to disclose all conflicts of interest and will establish a mechanism for the management of all reported dualities of interest.

APPENDIX A – CRITERIA OF HANNIFIN AND RAJKA

Hanifin and Rajka Diagnostic Criteria for Atopic Dermatitis (AD)

Major criteria: Must have three or more of:

1. Pruritus
2. Typical morphology and distribution
 - Flexural lichenification or linearity in adults
 - Facial and extensor involvement in infants and children
3. Chronic or chronically-relapsing dermatitis
4. Personal or family history of atopy (asthma, allergic rhinitis, atopic dermatitis)

Minor criteria: Should have three or more of:

1. Xerosis
2. Ichthyosis, palmar hyperlinearity, or keratosis pilaris
3. Immediate (type 1) skin-test reactivity
4. Raised serum IgE
5. Early age of onset
6. Tendency toward cutaneous infections (especially *S aureus* and herpes simplex) or impaired cell-mediated immunity
7. Tendency toward non-specific hand or foot dermatitis
8. Nipple eczema
9. Cheilitis
10. Recurrent conjunctivitis
11. Dennie-Morgan infraorbital fold
12. Keratoconus
13. Anterior subcapsular cataracts
14. Orbital darkening
15. Facial pallor or facial erythema
16. Pityriasis alba
17. Anterior neck folds
18. Itch when sweating
19. Intolerance to wool and lipid solvents
20. Perifollicular accentuation
21. Food intolerance
22. Course influenced by environmental or emotional factors
23. White dermographism or delayed blanch

## SAP Change History

Version	Date	Summary of Changes	Author
1	13DEC2019	Original document	[name]

## 1. LIST OF ABBREVIATIONS AND DEFINITIONS OF TERMS

AD	atopic dermatitis
AE(s)	adverse event(s)
ANCOVA	analysis of covariance
ATC	anatomical therapeutic chemical
AUS	Australia
BID	twice daily
BSA	Body Surface Area
CBC	Complete Blood Count
CBD	Cannabidiol
eCRF(s)	Electronic case report form(s)
CRO	Clinical research organization
g	grams
g/day	grams/day
IGA	Investigator's Global Assessment
IL	Interleukin
I-NRS	Itching-Numerical Rating Score
ITT	Intent-to-Treat
IWRS	Interactive Web-based Randomization System
kg	kilograms
LOCF	last observation carried forward
LSMean	least squares mean
MedDRA	Medical Dictionary for Regulatory Activities
mITT	modified Intent-to-Treat
n	number of observations
N	number of subjects (sample size)
NZ	New Zealand
PP	per-protocol
PT(s)	preferred term(s)
QST	QST Consultations, Ltd.
SAE(s)	serious adverse event(s)
SAS®	Statistical Analysis System (SAS® Institute Inc., Cary, NC)

SD	standard deviation
SOC	system organ class
TEAE(s)	treatment-emergent adverse event(s)
US	United States
WHO-DDE	World Health Organization Drug Dictionary

## 2. INTRODUCTION

Atopic dermatitis (AD) is an inflammatory cutaneous disease which may co-exist with other immunoglobulin E (IgE)-dependent atopic diseases such as allergic rhinitis, bronchial asthma, and food allergy. [14] The disease is a skin disorder which presents itself as itchy, inflamed, red, and possibly lichenified (i.e. thickened) skin with affected areas potentially distributed widely over the body. [13] The pathogenesis of the disease is thought to involve an acute T-helper 2 (Th2) cell response followed by a chronic response involving additional T-helper populations; although more recent research suggests that Th2 cells and a more generalized T-cell response are present during both acute and chronic phases. [6] The importance of Th2 cells and interleukin (IL)-4 and IL-13 signaling in the disease is supported by the effectiveness of dupilumab, a human monoclonal antibody specific to IL-4R $\alpha$  that can block IL-4 and IL-13 signaling, to improve many symptoms of AD including pruritus, and reduction in AD area and severity. [6]

Literature indicates that Cannabidiol (CBD) can inhibit the migration, proliferation and cell maturation processes involved in Th17, Th1, and Th2 immune responses. [9, 10, 11] These are considered critical immune pathways involved in the pathophysiology of AD. [8] CBD may have beneficial effects on AD due to direct antioxidant effects, and ability to improve antioxidant status in models of inflammation and autoimmune disease. [1, 2, 3, 4, 12, 5, 7, 11] Finally, CBD may also provide a therapeutic benefit for the treatment of AD by modulating the inflammatory response regulated by keratinocytes. CBD inhibited the production of monocyte chemotactic protein-2 (MCP-2), IL-6, IL-8, and tumor necrosis factor- $\alpha$  in polyinosinic-polycytidylic acid stimulated human keratinocyte (HaCaT) cells. [16] CBD has also been shown to directly inhibit the proliferation of keratinocytes. [17]

This study is the second study in evaluating the use of BTX 1204 4% (w/w) in subjects with AD.

Botanix Pharmaceuticals' BTX 1204 contains the active pharmaceutical ingredient, cannabidiol (CBD; 2-[(1R,6R)-6-isopropenyl-3-methylcyclohex-2-en-1-yl]-5-pentylbenzene-1,3-diol). CBD is a member of a broader family of compounds known as cannabinoids, a class of compounds originally derived from the cannabis sativa plant. [15]

The preliminary efficacy of BTX 1204 4% (w/w) was evaluated in a Phase 1b, randomized, double-blind, vehicle-controlled study. After only 4 weeks of treatment, subjects receiving BTX 1204 4% (w/w) had improvements in the Signs of AD score compared to treatment with Vehicle. A total of 34.8% of subjects receiving BTX 1204 had a  $\geq 4$ -point improvement in the Signs of AD score compared to 18.2% of subjects receiving vehicle. Improvement was observed primarily in erythema, exudation and lichenification.

This study is intended to establish safety, tolerability and efficacy in subjects with moderate AD treated twice daily (BID) with BTX 1204 4% (w/w) Liquid Formulation compared to subjects treated with Vehicle for 12 weeks.

### **3. STUDY OBJECTIVES**

The objective of this study is to determine the safety, tolerability and efficacy of BTX 1204 4% (w/w) in subjects with moderate atopic dermatitis.

### **4. STUDY DESIGN**

#### **4.1 Overall Study Design**

This is a randomized, double-blind, vehicle-controlled, Phase 2a study in subjects with moderate AD. Approximately two hundred (200) subjects randomized 1:1 (100 active: 100 vehicle) will be enrolled.

There will be two dose groups. All subjects will apply study drug for 84 days.

- BTX 1204 4% BID, or
- Vehicle BID

At the Baseline visit, qualified subjects will be randomized to treatment using an Interactive Web-based Randomization System (IWRS). The study will be a total of up to 112 days in duration; screening period (up to 28 Days), and 84 days of treatment. During the study, subjects will return to the study clinic at Days 15, 29, 57, and 84 (Study Exit).

#### **4.1.1 Schedule of Visits and Assessments**

The schedule of assessments can be found in Section 6.3.9 of the protocol.

#### **4.1.2 Method of Assigning Subjects to Treatment Groups**

A randomization schedule will be generated by a statistician(s) from QST Consultations, Ltd. (QST) Statistical Services department who is not associated with the day-to-day conduct of the study, using a validated system. The randomization list will not be stratified, but stratification by site will be accomplished within the IWRS.

Once a subject is deemed eligible to enroll, randomization will occur using an IWRS. The IWRS will assign a study drug kit number based on a predetermined randomization schedule. The kit number will be recorded in the electronic case report form (eCRF). Randomization will be 1:1 (100 active: 100 vehicle).

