9.2. Statistical Hypotheses

The purpose of this Phase 2a study is to describe the safety and efficacy of treatment with the BTX 1204 4% Liquid Formulation vs Vehicle with BID dosing in subjects with moderate atopic dermatitis. Exploratory analysis of the study drug's effect on AD will be evaluated. None of these assessments will use hypothesis testing to assess their treatment effect.

Should any post-hoc statistical analyses be conducted to present study outcomes, the methods for analysis will be described in the final clinical study report.

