9.5. Measures to Minimize Bias

9.5.1. Enrollment/Randomization/Masking Procedures

A randomization code will be prepared by an unblinded statistician. This statistician will be the only person aware of the randomization code. Randomization will be 1:1 (100 active: 100 vehicle) and done by site. Once a subject is deemed eligible to enroll, randomization will occur. The site will contact the IWRS to receive the kit/bottle number(s) to be used for that subject throughout the study.

Study drug, active or vehicle, will be labelled identically except for the kit/bottle numbers. All bottles of study drug will contain 100 mL of either BTX 1204 4% (w/w) Liquid Formulation or Vehicle. The vehicle study drug is indistinguishable from the active study drug.

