#### **6.1.4 Adjustments for Covariates**

Baseline total BSA affected by AD will be a covariate for the secondary efficacy endpoint, change from Baseline in total BSA affected by AD. Baseline Signs of AD total score will be a covariate for the secondary and exploratory efficacy endpoints change from Baseline in total Signs of AD. No other covariates are planned to be used in the analyses for this study.

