#### **6.1.7 Multicenter Studies**

This study will be conducted at multiple investigational sites in the United States (US), Australia (AUS) and New Zealand (NZ) with the intention of pooling the results for analysis.

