### **6.8.1 Primary Efficacy Analysis**

The proportion of subjects with IGA success defined as an IGA score of Clear (0) or Almost Clear (1) with at least a 2-grade improvement from Baseline at Day 85 will be analyzed using logistic regression with a term for treatment.

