#### **6.10.1 Repeated Measures**

The first sensitivity analysis for the primary endpoint, IGA success, will be analyzed using a repeated measures logistic regression (generalized estimating equations), with dichotomized IGA success as the dependent variable and treatment group, visit, and treatment group by visit interaction as independent factors. In this analysis, data from all post-Baseline visits will be included with no imputation for missing data.

```
proc genmod data = datain;
  class SUBJECT TRT VISIT;
  model IGA SUCCESS = TRT VISIT TRT * VISIT / dist=bin;
  repeated subject = SUBJECT/type = cs;
  lsmeans TRT*VISIT / diff;
  estimate 'pval' TRT 1 -1 TRT*VISIT 0 0 1 0 0 -1;
run;
```

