Table 14.1.4.4: Summary of Concomitant Antibiotic Therapies by ATC Level 2 Term and Preferred Name (Safety Population)

**Programming note:** Replace 3rd footnote with - Percentages are based on the number of subjects in each treatment group in the Safety population.

Table 14.2.1.1: Primary Efficacy Endpoint: Dichotomized IGA Success at Day 85  
(ITT Population)

	BTX 1204 4% BID (N=xxx)	Vehicle BID (N=xxx)	Treatment P-Value a
At Least a 2 Grade Improvement from Baseline and IGA Grade of 0 or 1			
n	xx	xx	
Success	xx ( xx.x%)	xx ( xx.x%)	
Failure	xx ( xx.x%)	xx ( xx.x%)	
Success a	xx.x%	xx.x%	x.xxx
Failure a	xx.x%	xx.x%	

a Estimates and p-value from a logistic regression with a term for treatment group.

Note: Missing values imputed using LOCF.

SOURCE: USERNAME\SPONSOR\PROJECT\JOBNAME (DATE,TIME)

Repeat Table 14.2.1.1 for the following:

Table 14.2.1.2: Primary Efficacy Endpoint: Dichotomized IGA Success at Day 85 (mITT Population)

Table 14.2.1.3: Primary Efficacy Endpoint: Dichotomized IGA Success at Day 85 (PP Population)

**Programming note:** *Replace last footnote with* - Note: No imputations were made for missing data.

Table 14.2.1.4: Sensitivity Analysis of Primary Efficacy Endpoint: Dichotomized IGA Success at Day 85  
(ITT Population)

	BTX 1204 4% BID (N=xxx)	Vehicle BID (N=xxx)	Treatment P-Value a
At Least a 2 Grade Improvement from Baseline and IGA Grade of 0 or 1			
n	xx	xx	
Success	xx ( xx.x%)	xx ( xx.x%)	
Failure	xx ( xx.x%)	xx ( xx.x%)	
Success a	xx.x%	xx.x%	x.xxx
Failure a	xx.x%	xx.x%	

a Estimates and p-value from a repeated measures logistic regression with .factors of treatment group, visit and treatment group by visit interaction.

Note: No imputations were made for missing data.

SOURCE: USERNAME\SPONSOR\PROJECT\JOBNAME (DATE,TIME)

Table 14.2.1.6: Subgroup Summary of the Primary Endpoint: Dichotomized IGA Success at Day 85  
(mITT Population)  
(Page 1 of 5)

			Geographical Region: US	
			BTX 1204 4% BID (N=xxx)	Vehicle BID (N=xxx)
At Least a 2 Grade Improvement from Baseline and IGA Grade of 0 or 1				
n			xx	xx
Success			xx ( xx.x%)	xx ( xx.x%)
Failure			xx ( xx.x%)	xx ( xx.x%)
			Geographical Region: AUS/NZ	
			BTX 1204 4% BID (N=xxx)	Vehicle BID (N=xxx)
At Least a 2 Grade Improvement from Baseline and IGA Grade of 0 or 1				
n			xx	xx
Success			xx ( xx.x%)	xx ( xx.x%)
Failure			xx ( xx.x%)	xx ( xx.x%)

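### Randomisation is stratified by site but no efficacy model includes site, and the planned tables give a p-value as the only comparison between arms

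*SAP*

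**What the plan says.** **Allocation.** Protocol 9.5.1: "Randomization will be 1:1 (100 active: 100 vehicle) and done by site". SAP 4.1.2: "The randomization list will not be stratified, but stratification by site will be accomplished within the IWRS". The SAP wording is awkward, but the two documents agree that site is a stratification factor.

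**Models.** Under SAP 6.8.1 the primary endpoint "will be analyzed using logistic regression with a term for treatment", and the other IGA endpoints follow it (6.8.2.2, 6.8.2.3, 6.9.1.3). The Signs of AD and BSA ANCOVAs contain the baseline value and treatment (6.8.2.1, 6.8.2.4, 6.9.1.1, 6.9.1.2, 6.9.1.4). The GEE in 6.10.1 contains treatment, visit and their interaction. SAP 6.1.4 closes the list: "No other covariates are planned to be used in the analyses for this study". On centres, SAP 6.1.7 says only that the study runs in three countries "with the intention of pooling the results for analysis". Region appears only as a descriptive subgroup (6.1.11).

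**Output.** The footnote of the primary shell, Table 14.2.1.1, reads "Estimates and p-value from a logistic regression with a term for treatment group"; the table holds percentages per arm and one p-value column. The ANCOVA shells hold an LS mean, an LS SD and a p-value. The GEE code requests differences ("lsmeans TRT*VISIT / diff"), but its shell, Table 14.2.1.4, does not print them.

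**Purpose.** Protocol 9.2 says of the efficacy assessments: "None of these assessments will use hypothesis testing to assess their treatment effect".

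**The concern.** Blocking within site makes the arms more alike than simple randomisation would. An analysis that ignores site still charges between-site variation to error, so its standard error is too large whenever sites differ. Differences are plausible for an investigator-rated endpoint across three countries. SAP Section 8 drops Baseline IGA on the ground that treatment was not stratified by it. By the same reasoning site, which is a stratification factor, belongs in the models.

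The output gap matters more. The size of the effect relative to vehicle, with its precision, is the main product of a study sized on clinical considerations alone. A p-value by itself does not supply it. The protocol also promises 95% CIs with its summaries (Protocol Summary and 9.3.1). SAP 6.1 and the shells leave them out, and Section 8 does not list the change. That promise covers the summaries, not the treatment difference.

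**Working it through.** **No plan figure to reproduce.** Protocol 9.4 and SAP 7 give 100 per arm and no power, effect size or site assumption. The number of sites, the block size and the between-site variance are not stated. Only 100 per arm below is a design figure; the rest are assumptions.

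**Main simulation (40,000 trials per setting).**
- Rates of 18.2% and 34.8%. These are the Phase 1b Signs of AD responder rates in Protocol 1.3.2, not IGA success.
- 10, 20 or 40 sites of unequal size, blocks of 4 within site, and sites under 8 subjects pooled within two regions.
- Site effect N(0, SD) on the logit scale, with intercepts solved so that the arm rates stay fixed as SD changes. Two-sided 5% level.
- Treatment-only Wald test: log OR / SE, with SE² = 1/a + 1/b + 1/c + 1/d over the four cells.
- Site-stratified CMH test: [Σ(x₁ − n₁t/n)]² / Σ[n₁n₀t(n − t) / (n²(n − 1))], summed over analysis sites, where x₁ is active-arm successes, t total successes and n site size.

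Ranges are over the numbers of sites. Null rejection uses 20% in both arms.

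| Site SD | Power, treatment-only | Power, CMH | Gain (points) | Null rejection, treatment-only | Mean 95% half-width of risk difference (points), unadjusted / stratified |
|---|---|---|---|---|---|
| 0 | 75.9–76.4% | 76.0–76.7% | about 0 | 4.5–4.8% | 11.95 / 11.97–11.98 |
| 0.5 | 76.3–76.7% | 77.4–78.0% | 0.9–1.3 | 4.2–4.4% | 11.88–11.94 / 11.70–11.81 |
| 1.0 | 77.4–77.7% | 80.5–81.7% | 2.8–4.1 | 3.5–3.7% | 11.75–11.90 / 11.07–11.42 |

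Null rejection for CMH was 4.7–5.0% throughout. The usual two-proportion formula gives 76.2% power for these rates, in line with the SD 0 row.

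**Sensitivity.**
- Other rate pairs at 20 sites (10/25%, 20/35%, 30/50%): gains of −0.3 to 0.7, 0.7 to 1.5 and 3.0 to 4.7 points at SD 0, 0.5 and 1.0.
- Twenty equal sites, perfectly balanced, no pooling, 15% against 30%: 72.4% vs 72.7%, 72.1% vs 73.9% and 73.5% vs 78.5%.
- Forty unequal sites without pooling: CMH loses 2.1 points at SD 0 and 0.6 at SD 0.5.

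**Continuous endpoints.** With balance within site and intraclass correlation r between sites, the true variance of the difference is (1 − r) times what the unadjusted model assumes. If the site-adjusted test has 80% power, the unadjusted power is Φ(1.96 + 0.84 − 1.96/√(1 − r)) and the type I error is 2[1 − Φ(1.96/√(1 − r))]:

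| r | Unadjusted power | Type I error |
|---|---|---|
| 0 | 80.0% | 0.050 |
| 0.05 | 78.5% | 0.044 |
| 0.10 | 76.9% | 0.039 |
| 0.20 | 72.9% | 0.028 |

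**What the primary table would and would not show.** Take 35/100 against 18/100.
- OR = (35/65)/(18/82) = 2.45, so log OR = 0.897.
- SE = √(1/35 + 1/65 + 1/18 + 1/82) = 0.334, giving p = 0.007.
- 95% CI for the OR = exp(0.897 ± 1.96 × 0.334) = 1.27 to 4.72.
- Risk difference = 0.350 − 0.180 = 0.170, with half-width 1.96 × √(0.35 × 0.65/100 + 0.18 × 0.82/100) = 0.120, so 5.0 to 29.0 points.

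The shell prints 35.0%, 18.0% and the p-value only.

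**The case against.** The strongest reply is that this is a small, declared choice. Sites are pooled openly, the tests are exploratory, no power is claimed, and omitting site biases nothing. That stands, and it means the site point is about efficiency, not validity.

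The size of the gain is also uncertain. Every site input is assumed, and the comparison changes the test as well as the stratification. At an assumed 5% against 15%, CMH gains about 3 points even with no site effect (64.2% to 67.4%), because it replaces a Wald test. At low IGA success rates, part of any gain would therefore not be due to site. Logistic regression with site was not simulated.

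On output, the odds ratio, the risk difference and their intervals can be worked out from the printed counts of the primary table, because the model is treatment-only. No information is lost there. The same cannot be done for the GEE, and the ANCOVA shells plan no adjusted difference, standard error or CI. Their LS mean rows show a single value, which may be an effect of text extraction, but the label is a least squares mean, not a difference.

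Finally, Protocol 9.3.7 allows exploratory tests, so a p-value is not forbidden. It sits uneasily with Protocol 9.2, and neither section supports it as the only comparative result.

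**Conclusion.** Both parts hold. Site is a stratification factor and appears in no efficacy model. The effect is conservative: no material loss if sites do not differ, and roughly 1 point of power at site SD 0.5 and 3 to 4 points at SD 1.0 for 18.2% against 34.8%. Those sizes depend on the assumed rates, site numbers and pooling; the equal-site runs put them nearer 2 and 5 points. The missing between-arm estimates and intervals rest on the shells alone and are the more important defect. Neither threatens validity, but both should be corrected before unblinding.

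The shells also carry footnote errors. Tables 14.2.2.2.1 and 14.2.3.5.1 cite adjustment for Baseline IGA, against SAP 6.8.2.2, 6.8.2.3, 6.9.1.3 and Section 8; the term is inert because eligibility requires IGA 3. Table 14.2.3.3.1 names Baseline Signs as the covariate for a BSA model, against SAP 6.9.1.2.

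**What to change.** - Analyse the primary and other binary endpoints by CMH stratified by analysis site, or by logistic regression with analysis site. Fix before unblinding a rule that pools small sites within country.
- Add analysis site to the Signs and BSA ANCOVAs.
- Print the stratified risk difference or odds ratio with 95% CI in the primary, secondary and GEE tables, and LS mean differences with 95% CI in the ANCOVA tables.
- Restore the protocol's 95% CIs for summaries, or list their removal in SAP Section 8.
- Remove the Baseline IGA wording from the footnotes of Tables 14.2.2.2.1 and 14.2.3.5.1, and name Baseline BSA in Table 14.2.3.3.1. Also reconcile the days in that table: its title says 15, 29 and 85, its body shows 29, 57 and 57, and SAP 6.9.1.2 says 15, 29 and 57.

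The cost is SAP wording and extra table columns, with no new data. The one risk is many small sites. With pooling, power at site SD 0 changed by less than 1 point in the main simulation and the three other rate pairs run with it; without pooling, about 2 points could be lost.
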